
The study will determine for the first time based on real-time tumor positioning information whether patients are able to reproducibly hold their breath in DIBH within excursions of 5.+-0.5cm or less. Furthermore, it will determine whether visual biofeedback improves the reproducibility of the breathhold. It will provide a unique dataset that will allow us to determine the concordance level of real-time tumor position information from the Calypso transponders, external surface signal and radiographic imaging. Ultimately, this study will allow us to quantify the decrease in radiation dose to organs at risk, decreased toxicity and amount of dose escalation made possible by the DIBH maneuver using real-time tumor position information.

Patients will be considered evaluable for protocol when they have had successful calypso beacon implantation without the beacons migrating> 5cm, and they have completed training in DIBH. In the extension of the protocol described below, 25 patients will be accrued; the expected time for completion of this study is 3 year from its approval.

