12.0 CRITERIA FOR THERAPEUTIC RESPONSE/OUTCOME ASSESSMENT

Primary objectives:

- To evaluate the feasibility of Calypso transponders as an internal tumor surrogate to guide DIBH radiation treatments in real time.
- Feasibility is defined as completion of all treatments using the DIBH treatment plan and Calypso transponders. Patients who cannot have their transponders placed accurately bronchoscopically or for whom Calypso-guided DIBH will not be possible will be considered a failure. Patients who are removed from the protocol as a result of being unable to perform the breath hold for 3 consecutive treatment days at any point in the treatment course for reasons that are not related to the Calypso transponders, Calypso detection or complications of using the Calypso implantation or system (e.g. disease progression, severe side effects from treatment, e.g. esophagitis, infections, failure to thrive, generalized weakness, low blood counts etc.), will be replaced by new evaluable patients. Those patients will be treated with the free-breathing backup radiation treatment plan. The reason for the patient's inability to hold their breath will be recorded.

Secondary objectives:

- To compare the reproducibility with visual versus without visual biofeedback.
- To assess differences in the ability of maintaining the DIBH maneuver within the fate with and without visual biofeedback
- To measure the residual intrafraction tumor motion and associated improvement in normal tissue dosimetry during DIBH based on the Calypso lung transponder signal as a surrogate

- To measure the increase in dose escalation and the potential for decreasing margins made possible by Calypso-guided DIBH
- To determine the minimum clinically feasible gate margin for radiation
- To assess tumor shrinkage, beacon position and centroid changes in conventionally fractionated patients
- To assess intra- and inter-fraction variation in lung volume preservation of multiple DIBH maneuvers

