14.0 BIOSTATISTICS

The primary objective of this nonrandomized study is to test the feasibility of anchored Calypso transponders to guide and monitor DIBH radiation treatments. Feasibility is defined as patients being able to successfully complete the course of treatment. Patients who cannot have their transponders placed accurately bronchoscopically and for whom Calypso-guided DIBH will not be possible as a consequence of that will be considered a failure. Patients who are removed from the protocol as a result of being unable to perform the breath hold for 3 consecutive treatment days at any point in the treatment course for reasons that are not related to the Calypso transponders, Calypso detection or complications of using the Calypso implantation or system (e.g. disease progression, severe side effects from treatment, e.g. esophagitis, infections, failure to thrive, generalized weakness, low blood counts etc.), will be replaced by new evaluable patients. The patients who are removed will be treated with the free-breathing backup radiation treatment plan. The reason for the patient's inability to hold their breath will be recorded.

For this objective the first and second set of 25 evaluable patients will be stratified and analyzed separately. Some details are provided below.

We will enroll 30 patients upfront and we expect that at least 25 evaluable (DIBH training can be done and Calypso beacons can be implanted without migrating > 5cm) patients can be used in

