assessing the feasibility rate. To establish the decision rule we will compute the sample feasibility rate (i.e., the number of patients who could be successfully treated divided by the total number of evaluable patients, which we expect to range from 25 to 30) and form an 80% 2-sided Clopper-Pearson exact confidence interval. If the lower bound of this exact confidence interval is greater than 66% then we will declare this procedure feasible. Namely, we will test the hypotheses $H_0: \theta \leq 0.66$ vs. $H_1: \theta > 0.66$ at $\alpha=0.05$, where θ denotes the feasibility rate. The test statistic will be the lower bound of the 90% 2-sided Clopper-Pearson exact confidence interval for binomial trials. Equivalently, this test statistic can be written as $\text{Beta}(0.05, X, N+1-X)$, i.e., the 5th-percentile of the beta distribution with two parameters X and $N+1-X$, where X and N denote the number of successes and the total sample size (expected to be from 25 to 30), respectively. When the sample size is as small as 25, the power of rejecting the null hypothesis is 61%, 84% and 97% when the true feasibility rate is 0.80, 0.85 and 0.90, respectively. When the sample size is as large as 30, such power becomes 61%, 85% and 97%. Since we expect the feasibility rate to be around 0.85, the sample size is sufficiently large. We expect to finish the recruitment in 4 years.

For protective purposes we will implement a stopping rule to prevent excessive rate of pneumothorax or hospitalization (related to the proposed procedure). If 6 or more events (i.e., procedure-related pneumothorax or hospitalization) among the first 30 patients, or 11 or more events among the total 55 patients we plan to enroll are observed, we will halt the trial to thoroughly investigate such events. This sequential stopping rule has the following probability of halting the trial:

True event probability	0.05	0.08	0.10	0.15	0.20	0.25	0.30
Probability of halting the trial	0.003	0.030	0.081	0.342	0.679	0.900	0.978

In addition, a second stopping rule will be implemented if a maximum of two device migrates to a critical organ, such as the heart or brain, or if one device-related death is observed.

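### Patients without successful transponder implantation are defined as feasibility failures, yet the primary feasibility rate divides by a population that excludes them

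*Combined protocol and SAP*

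**What the plan says.** **Who is a failure.** Section 12.0: "Patients who cannot have their transponders placed accurately bronchoscopically or for whom Calypso-guided DIBH will not be possible will be considered a failure". Section 14.0 is narrower. It names as failures "Patients who cannot have their transponders placed accurately bronchoscopically and for whom Calypso-guided DIBH will not be possible as a consequence of that".

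**Who is evaluable.** Section 1.0: "Patients will be considered evaluable for protocol when they have had successful calypso beacon implantation", with no beacon migration beyond 5 cm and with DIBH training completed. Section 14.0 gives the same conditions in brackets, asking that training can be done and that beacons can be implanted without migrating more than 5 cm.

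**What is divided by what.** Section 14.0 defines the rate as "the number of patients who could be successfully treated divided by the total number of evaluable patients" and expects 25 to 30 evaluable patients. The procedure is declared feasible if the Clopper-Pearson lower bound exceeds 66%. The paragraph names an 80% two-sided interval in one sentence and a 90% two-sided interval in another.

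**The two sets.** "For this objective the first and second set of 25 evaluable patients will be stratified and analyzed separately". For the first set: "We will enroll 30 patients upfront and we expect that at least 25 evaluable". The extension accrues 25 (Sections 1.0 and 9.0), and the stopping rule refers to "11 or more events among the total 55 patients we plan to enroll". Patients removed because they cannot hold their breath, for reasons unrelated to Calypso, "will be replaced by new evaluable patients". No replacement is stated for other losses.

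**The concern.** The failure definition and the denominator do not fit together. If implantation does not succeed, Sections 12.0 and 14.0 call the patient a failure, while the evaluability condition takes the same patient out of the count. Taken literally, the stated formula removes a class of defined failures.

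The error runs one way. Each such patient leaves the denominator without leaving the numerator, so the rate and its lower bound can only rise. This is the primary endpoint of a feasibility study of an implanted device, and whether the device can be placed is part of the question. With 25 to 30 patients and a fixed threshold, one or two patients can decide the result. If the text stays as it is, the denominator may be chosen after the data are seen.

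**Working it through.** **Inputs from Section 14.0.** Threshold 0.66; N from 25 to 30; expected feasibility 0.85; 30 enrolled upfront; 55 in total. The documents give no placement-failure rate for this trial, so every such rate below is an assumption.

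**Rule.** With X successes in N patients, the lower bound is L(X, N) = the a-quantile of Beta(X, N+1−X), where a = 0.10 for the 80% interval and 0.05 for the 90% interval. Declare feasible if L > 0.66.

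**The plan's own power figures.** With a = 0.10 the cut-offs are 20/25 and 24/30.

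| N | Interval | Cut-off | Power at 0.80 / 0.85 / 0.90 | Plan states |
|---|---|---|---|---|
| 25 | 80% | 20 | 61.7 / 83.8 / 96.7% | 61 / 84 / 97% |
| 30 | 80% | 24 | 60.7 / 84.7 / 97.4% | 61 / 85 / 97% |
| 25 | 90% | 21 | 42.1 / 68.2 / 90.2% | not matched |
| 30 | 90% | 25 | 42.8 / 71.1 / 92.7% | not matched |

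The printed powers belong to the 80% interval, so that interval leads below and the 90% result is given alongside.

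**Does the denominator change the decision?** Compare L(X, N−k) with L(X, N), where k patients had no successful implantation.

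| Enrolled | k | Interval | Success counts that change from fail to pass when the k are dropped |
|---|---|---|---|
| 30 | 1 | 80% | 23: 23/29 = 79.3%, L = 0.665; 23/30 = 76.7%, L = 0.639 |
| 30 | 1 | 90% | 24: 24/29, L = 0.671; 24/30, L = 0.643 |
| 30 | 3 | 80% | 22 and 23 |
| 30 | 3 | 90% | 23 and 24 |
| 25 | 1 | either | none |
| 25 | 2 | 80% | 19: 19/23, L = 0.682; 19/25, L = 0.617 |
| 25 | 2 | 90% | 20: 20/23, L = 0.696; 20/25, L = 0.625 |

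**Chance of a wrong declaration.** Let placement fail with probability q and let the success rate counting those failures be exactly 0.66. The rate among implanted patients is then 0.66/(1−q). With c(n) the cut-off at n, the chance of declaring feasibility when failures are dropped is

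Σₖ P(Bin(N, q) = k) × P(Bin(N−k, 0.66/(1−q)) ≥ c(N−k)).

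| Enrolled, interval | q = 2% | q = 5% | q = 10% | Failures kept |
|---|---|---|---|---|
| 30, 80% | 10.0% | 14.1% | 25.2% | 7.3% |
| 30, 90% | 4.8% | 8.0% | 15.3% | 3.0% |
| 25, 80% | 10.5% | 13.2% | 21.9% | 9.9% |
| 25, 90% | 4.2% | 5.6% | 11.2% | 4.0% |

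**Power once failures are kept.** If 0.85 is the rate among implanted patients and q = 5%, the rate counting failures is 0.85 × 0.95 = 0.8075. With 30 enrolled, P(Bin(30, 0.8075) ≥ 24) = 64.7% under the 80% interval, against 84.7% at 0.85.

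**Second set.** 55 − 30 = 25 places for a set described as 25 evaluable. The chance that all 25 are evaluable is (1 − loss)^25: 60%, 28% and 7% at assumed losses of 2%, 5% and 10%.

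**The case against.** **Not every poor placement leaves the rate.** Section 14.0's failure clause concerns inaccurate placement that makes Calypso-guided DIBH impossible. Its evaluability condition asks only that beacons can be implanted without migrating more than 5 cm. A patient with beacons in place but badly positioned can be evaluable and a failure, and so stay in the denominator. Section 9.0 also permits two transponders where three are not possible. A reader might infer that all placement failures drop out, but the documents do not support that. The clear conflict is confined to patients without successful implantation. The word successful in Section 1.0 leaves the boundary open. This objection narrows the point without removing it.

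**The effect may be small.** At 2% placement failure the excess is about 3 percentage points with 30 enrolled and under 1 point with 25 (80% interval). Reversals need specific success counts. An assumed 16.7% placement failure (5 of 30) gives a 50% chance of wrong declaration with 30 enrolled, but it assigns to placement all the loss that the 30-for-25 allowance permits, including training and migration losses. It is an extreme and should not be read as the expected size.

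**The second set.** A reader might infer an arithmetic error, or an underpowered second test. Neither is established. The first set's 25 is itself nominal, since N of 25 to 30 is expected. Breath-hold ability is an entry criterion, which should limit training losses. Most of the shortfall disappears if failed placements stay in the denominator. The natural reading of separate analysis followed by one rule is that the rule applies to each set, and it yields a cut-off for any N. What is missing is a confirming sentence.

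**Conclusion.** The point holds for patients without successful implantation: they are failures by definition and absent from the rate by definition, which biases the primary result upward. It holds under either interval, so it does not depend on how the 80%/90% discrepancy is resolved. With 30 enrolled, one such patient is enough to reverse the decision at one success count; with 25 enrolled, it takes two. Under the 80% interval with 30 enrolled, the chance of declaring feasibility at a rate of exactly 0.66 rises from 7% to between 10% and 25% over assumed placement failure of 2% to 10%. These sizes rest on assumed rates, on independence between patients, and on reading every failed placement as non-evaluable; if some are kept as evaluable failures, the effect is smaller. The second-set size and the scope of the rule are minor matters of wording.

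**What to change.** 1. In Sections 1.0, 12.0 and 14.0, define the denominator as every patient in whom bronchoscopic placement was attempted, with failed placement counted as a failure. Keep the existing replacement of breath-hold removals unrelated to Calypso as a stated exception. Use one failure wording in Sections 12.0 and 14.0.
2. Report the rate among successfully implanted patients, with its exact interval, as a secondary figure.
3. Section 4.1 refers to successful localization in the first 25 patients, so first-set results may already be known. If they are, report both denominators for that set and date the change, so that it is visible as one made with data in hand.
4. Describe the second set as 25 enrolled, up to 25 evaluable, because 30 + 25 = 55 leaves no allowance. Add one sentence saying whether the 66% rule applies to it or whether its result is estimation only.

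The cost is wording, with no extra patients and no change to treatment. The downside is less favourable stated power: in the 5% example above, 65% with 30 enrolled in place of 85% (80% interval).

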4.0 OVERVIEW OF STUDY DESIGN/INTERVENTION

4.1 Design

The primary objective of this study is to evaluate the feasibility of Calypso transponders as an internal tumor surrogate to guide DIBH radiation treatments in real time.

The use of Calypso transponders has the potential to result in improved reproducibility of tumor positioning during DIBH treatments. We therefore plan to analyze the obtained respiratory traces from the Calypso signal as well as the imaging data from CBCTs and radiographs to explore a set of secondary objectives. These include a comparison of the reproducibility of DIBH tumor position with visual versus without visual biofeedback (for patients who agree to use the digital goggles), measurement of any residual intrafraction tumor motion, improvement in normal tissue dosimetry during DIBH based on the Calypso lung transponder signal as a surrogate, and determination of any increase in dose escalation and the potential for decreasing margins made possible by Calypso-guided DIBH. Given the successful radiation localization in the first 25 patients, we will also aim to determine the minimum clinically feasible gate margin for radiation. We will reduce the gate from +/-5mm by 1mm for every 5 patients treated. Once the minimum gate is determined, the remaining patients will be treated at +1mm from this value. We will also plan to enroll at least 10 additional conventionally fractionated patients to assess the impact of tumor shrinkage on beacon position and centroid changes. Finally, lung volume preservation will be assessed on wide field of view cone-beam CTs and compared intra- and interfraction within each patient to check for reproducibility or variability of lung volumes across multiple DIBH maneuvers.

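### Patients whose transponders cannot be implanted are failures by definition, but the feasibility rate divides only by implanted patients and so leaves them out

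*Combined protocol and SAP*

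**What the plan says.** Two statements in the plan govern who counts in the primary endpoint.

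**Failure definition.** Section 12.0: "Patients who cannot have their transponders placed accurately bronchoscopically or for whom Calypso-guided DIBH will not be possible will be considered a failure". Section 14.0 starts the same way but joins the two conditions differently: placement is not accurate "and for whom Calypso-guided DIBH will not be possible as a consequence of that". Under either wording, a patient who cannot be implanted and so cannot have guided treatment is a failure.

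**Rate.** Section 14.0 defines the sample feasibility rate as "the number of patients who could be successfully treated divided by the total number of evaluable patients", with the denominator expected to lie between 25 and 30. Evaluable is defined twice. Section 1.0: "Patients will be considered evaluable for protocol when they have had successful calypso beacon implantation without the beacons migrating> 5cm", plus completed breath-hold training. Section 14.0, on the 30 patients enrolled first, expects at least "25 evaluable (DIBH training can be done and Calypso beacons can be implanted without migrating > 5cm) patients can be used in" the assessment of feasibility.

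The same basis carries over to the extension: "the first and second set of 25 evaluable patients will be stratified and analyzed separately". Section 1.0 describes that extension by total accrual: "In the extension of the protocol described below, 25 patients will be accrued".

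**The concern.** The primary question is whether anchored transponders can feasibly guide breath-hold treatment. Failed implantation is one way in which they cannot, and the protocol says so. Yet evaluability requires implantation to have succeeded already. The rule against 0.66 therefore tests the rate among implanted, trained patients, not the rate that the failure definition implies.

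Nothing in the plan puts the unimplanted patient back. The sentence in Section 13.0 on using acquired data covers only patients removed after part of their treatment. The replacement rule in Sections 12.0 and 14.0 covers only breath-hold removals unrelated to the Calypso system.

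One analyst following the denominator and another following the failure sentence could reach opposite decisions from the same data.

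Migration of more than 5 cm also makes a patient non-evaluable. That exclusion can bias either way: upward if guidance was lost, downward if the patient was still tracked and finished treatment.

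**Working it through.** **Inputs (Section 14.0).** Null rate 0.66; expected rate 0.85; evaluable N from 25 to 30. Two decision rules are stated, an 80% and a 90% two-sided Clopper-Pearson interval, so both are shown.

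**Formula.** Lower bound L = Beta(a; X, N+1−X), with a = 0.10 for the 80% interval and a = 0.05 for the 90% interval. Feasible if L > 0.66. Let c(N) be the smallest X that passes.

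**The plan's own figures first.** Power at true rates 0.80 / 0.85 / 0.90:

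| | N = 25 | N = 30 |
|---|---|---|
| Stated | 61 / 84 / 97% | 61 / 85 / 97% |
| 80% rule, c = 20 and 24 | 61.7 / 83.9 / 96.7% | 60.7 / 84.7 / 97.4% |
| 90% rule, c = 21 and 25 | 42.1 / 68.2 / 90.2% | 42.8 / 71.1 / 92.7% |

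The stated power is that of the 80% rule.

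**Cut-offs c(N).**

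| N | 23 | 24 | 25 | 26 | 27 | 28 | 29 | 30 |
|---|---|---|---|---|---|---|---|---|
| 90% rule | 20 | 21 | 21 | 22 | 23 | 23 | 24 | 25 |
| 80% rule | 19 | 20 | 20 | 21 | 22 | 23 | 23 | 24 |

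**Adding excluded failures to the denominator.**

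| Rule | Evaluable only | L | Failures added | L | Decision |
|---|---|---|---|---|---|
| 90% | 21/25 | 0.670 | 21/26 | 0.637 | reverses |
| 80% | 20/25 | 0.660 | 20/26 | 0.630 | reverses |
| 90% | 25/29 | 0.712 | 25/30 | 0.681 | stands |
| 80% | 25/29 | 0.743 | 25/30 | 0.713 | stands |
| 90% | 20/23 | 0.696 | 20/25 | 0.625 | reverses |
| 80% | 19/23 | 0.682 | 19/25 | 0.617 | reverses |

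**Chance of a reversal, given k excluded failures.** With A attempts and n = A − k evaluable, this is P(c(n) ≤ X < c(A)), X ~ Bin(n, 0.85):

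| Attempts | k | 90% rule | 80% rule |
|---|---|---|---|
| 30 | 1 | 18% | 13% |
| 30 | 2 | 39% | 18% |
| 25 | 1 | 0 | 0 |
| 25 | 2 | 23% | 20% |

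The 25-attempt rows apply to the second set if 25 patients are accrued in total. One exclusion cannot matter there because the cut-off is the same at 24 and 25. If accrual runs on to 25 evaluable patients, the 25-to-26 examples apply instead.

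**False declaration of feasibility.** Set the true rate over all 30 attempts to 0.66, with placement success q (assumed) and placement failure as the only exclusion. Evaluable N ~ Bin(30, q), and the success rate among evaluable patients is 0.66/q:

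| q | 90% rule | 80% rule |
|---|---|---|
| 1.00 | 3.0% | 7.3% |
| 0.95 | 8.0% | 14.1% |
| 0.90 | 15.3% | 25.2% |

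With all 30 in the denominator, the probabilities stay at 3.0% and 7.3%.

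**The case against.** The evaluable denominator is prespecified, and N and power are built on it. A rate conditional on implantation is a legitimate quantity, and the sentence calling these patients failures could be read as placing them in the count. On that view the text is ambiguous rather than biased. But the plan names placement failure as an endpoint failure, and both rules cannot govern one estimate.

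The failure wording concerns accurate placement, while evaluability in Section 14.0 requires only implantation without large migration. A patient with poorly placed beacons could be evaluable and counted as a failure. This stands, and it limits the point to patients in whom implantation is not achieved.

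Such patients should be few. Section 6.1 requires CT confirmation that placement is possible, Section 5.0 a confirmed pre-operative plan, and Section 9.0 accepts two transponders. The reversal probabilities above are also conditional on failures having occurred. Averaged over Bin(30, f) failures, with 0.85 among evaluable patients, the chance of reversal is about 11% (90% rule) and 7% (80% rule) at an assumed f of 2%, and 25% and 18% at 5%. At 2%, no failure occurs in 0.98^30 = 55% of 30-attempt sets. For 25 attempts at 2%, the chance of reversal is about 2% under either rule. This too stands: it bears on size, not on the contradiction.

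**Conclusion.** The concern holds. The failure definition and the denominator contradict each other for patients who cannot be implanted. Read as written, the rate is too high by the protocol's own definition whenever such a patient occurs. The bias is zero if every attempt succeeds and otherwise of unknown size, since no per-patient implantation failure rate is given. A result near the expected 0.85 can survive one exclusion, as 25/29 to 25/30 does; a borderline result can reverse on one. The reversal figures assume 0.85 among evaluable patients, and the false-declaration figures rest on assumed placement success. Because the defect lies in the primary decision rule, it must be fixed.

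**What to change.** - Make the primary denominator every patient in whom implantation is attempted, apart from those replaced under the existing rule for removals unrelated to Calypso.
- Count as failures patients whose transponders cannot be placed accurately or whose migration prevents Calypso guidance. Judge migrated but still tracked patients on treatment completion.
- List patients who leave before any attempt separately, with reasons.
- Use one failure definition in Sections 12.0 and 14.0, state whether a breath-hold training failure after implantation counts, and apply the same rule to both sets.
- Report the evaluable-only rate as secondary.
- Section 4.1 suggests that first-set results may be known ("Given the successful radiation localization in the first 25 patients"). If so, disclose the change as post hoc for that set and show both rates.
- State whether the expected 0.85 includes placement failures, and restate power if it does not.

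**Cost.** Wording in Sections 1.0, 12.0 and 14.0, one secondary table and possibly the post hoc disclosure; no extra procedures. The rate becomes less favourable if any placement fails. If 0.85 already includes placement failures, no power is lost against the stated plan. If it is conditional on implantation, power is P(Bin(N, 0.85 × (1 − f)) ≥ c(N)). With f assumed:

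| Attempts, rule | f = 0 | 2% | 5% |
|---|---|---|---|
| 30, 80% | 84.7% | 77.5% | 64.7% |
| 30, 90% | 71.1% | 61.5% | 46.9% |
| 25, 80% | 83.8% | 77.1% | 65.3% |
| 25, 90% | 68.2% | 59.2% | 45.8% |

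### The primary feasibility rule is stated at two error levels, and the quoted power belongs to the looser one: at alpha 0.05, power at a true rate of 0.85 is 68% (N=25) and 71% (N=30), not 84% and 85%

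*Combined protocol and SAP*

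**What the plan says.** All the conflicting statements stand in one paragraph of section 14.0 (Biostatistics).

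- The decision rule is first given as: "form an 80% 2-sided Clopper-Pearson exact confidence interval". The criterion follows: "If the lower bound of this exact confidence interval is greater than 66% then we will declare this procedure feasible".
- The next sentence presents the same rule as a test of H0: θ ≤ 0.66 against θ > 0.66 at α = 0.05, and adds: "The test statistic will be the lower bound of the 90% 2-sided Clopper-Pearson exact confidence interval for binomial trials". This bound is then written as the 5th percentile of a beta distribution with parameters X and N+1−X.
- For 25 evaluable patients, "the power of rejecting the null hypothesis is 61%, 84% and 97% when the true feasibility rate is 0.80, 0.85 and 0.90, respectively". For 30, the figures given are 61%, 85% and 97%.
- The conclusion drawn is: "Since we expect the feasibility rate to be around 0.85, the sample size is sufficiently large".

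The paragraph serves twice, because section 14.0 also says: "For this objective the first and second set of 25 evaluable patients will be stratified and analyzed separately". Section 4.1 introduces the extension with the words "Given the successful radiation localization in the first 25 patients". Section 1.0 accrues 25 further patients, and section 14.0 puts total enrolment at 55.

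**The concern.** The lower limit of an 80% two-sided interval leaves 10% in the lower tail, and that of a 90% interval leaves 5%. The plan presents them as one test. Alpha, the 90% interval and the beta percentile agree with each other at 0.05. The 80% sentence disagrees with them, and the power figures have to belong to one or the other.

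This rule produces the trial's primary verdict. If the two versions need different numbers of successes, a result in between is feasible under one sentence and not feasible under the next. The wording in section 4.1 also suggests that some first-set results were known when the extension was written. An open choice between the rules could then be settled after seeing data.

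**Working it through.** **Inputs (all from section 14.0).** Null rate 0.66; N from 25 to 30; lower-tail probability t = 0.10 (80% interval) or t = 0.05 (90% interval); true rates 0.80, 0.85 and 0.90.

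**Formulas.** The Clopper-Pearson lower bound is L(X) = Beta(t, X, N+1−X). The cut-off r is the smallest X with L(X) > 0.66. The exact type I error is P(Bin(N, 0.66) ≥ r), and power is P(Bin(N, θ) ≥ r).

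**Step 1: reproduce the plan's figures.**

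| Rule | N | r | Lower bound at r | Exact type I error | Power at 0.80 / 0.85 / 0.90 |
|---|---|---|---|---|---|
| 80% interval | 25 | 20 | 0.6603 | 0.099 | 61.7 / 83.8 / 96.7% |
| 80% interval | 30 | 24 | 0.6753 | 0.073 | 60.7 / 84.7 / 97.4% |
| Plan's quoted power | 25 | – | – | – | 61 / 84 / 97% |
| Plan's quoted power | 30 | – | – | – | 61 / 85 / 97% |

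All six quoted figures agree with the 80% rule to within one point.

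**Step 2: apply the stated alpha of 0.05.**

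| Rule | N | r | Lower bound at r | Exact type I error | Power at 0.80 / 0.85 / 0.90 |
|---|---|---|---|---|---|
| 90% interval | 25 | 21 | 0.6704 | 0.040 | 42.1 / 68.2 / 90.2% |
| 90% interval | 30 | 25 | 0.6810 | 0.030 | 42.8 / 71.1 / 92.7% |

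None of the six quoted figures is reproduced. At 0.85 the shortfall is 84 − 68 = 16 points (N=25) and 85 − 71 = 14 points (N=30).

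**Step 3: every N in the planned range.**

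| N | r, 80% interval | Type I error, 80% | Power at 0.85, 80% | r, 90% interval | Power at 0.85, 90% | Count with opposite verdicts | Its probability at 0.85 |
|---|---|---|---|---|---|---|---|
| 25 | 20 | 0.099 | 83.8% | 21 | 68.2% | 20 | 0.156 |
| 26 | 21 | 0.079 | 81.5% | 22 | 65.0% | 21 | 0.165 |
| 27 | 22 | 0.063 | 79.0% | 23 | 61.9% | 22 | 0.172 |
| 28 | 23 | 0.049 | 76.5% | 23 | 76.5% | none | 0 |
| 29 | 23 | 0.091 | 86.7% | 24 | 73.8% | 23 | 0.129 |
| 30 | 24 | 0.073 | 84.7% | 25 | 71.1% | 24 | 0.137 |

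Example: 20/25 has a lower bound of 0.660 under the 80% interval (above 66%, feasible) and 0.625 under the 90% interval (not feasible). For 24/30 the bounds are 0.675 and 0.643.

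**Step 4: the second set (a separate, smaller point).** The plan expects 25 to 30 evaluable patients from 30 enrolled. Assuming the same ratio for the extension, 25 × 25/30 = 20.8 to 25 × 30/30 = 25, so about 21 to 25 evaluable.

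| N | Power at 0.85, 90% interval | Power at 0.85, 80% interval |
|---|---|---|
| 21 | 61% | 61% |
| 22 | 58% | 77% |
| 23 | 54% | 74% |
| 24 | 50% | 71% |
| 25 | 68% | 84% |

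**The case against.** - **Limited reach.** This is a nonrandomized feasibility study, and the rules disagree on at most one count per N. A one-sided 0.10 level may be quite acceptable. That is true, but the plan chose a formal test with a fixed threshold, and the disputed count is a likely one at the rate the plan expects.
- **A scanning error.** The text has misread characters elsewhere, so 80% could be a misread 90%. This is unlikely, since the power figures match 80%. If it were so, the quoted power would still be wrong for the only rule left.
- **Other intervals.** A Wald bound with a 0.05 tail gives the same cut-offs (20/25 and 24/30). The plan names Clopper-Pearson, however, and those cut-offs have true type I errors of 0.099 and 0.073.
- **No power target.** Section 14.0 never promises 80% power. This stands: any statement about reaching 80% uses a conventional yardstick. The narrower point remains that the claim of a sufficient sample size follows power figures that do not belong to the alpha 0.05 test.
- **Results already seen.** Successful localization is not the primary endpoint, and section 14.0 still describes the first set in the future tense. No first-set success count is given. The concern is a reason to document the choice, not evidence of misuse.
- **Replacement.** Sections 12.0 and 14.0 replace patients removed for breath-hold failure unrelated to the transponders. This softens the second-set point, but it does not clearly cover failed implantation or beacon migration.

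**Conclusion.** The concern holds. The primary rule is written at one-sided 0.10 and at one-sided 0.05, and no other section says which governs. Between the two intervals the plan names, the quoted power fits only the 80% one.

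- If the 80% interval governs, the stated alpha, the 90% interval and the beta formula are wrong. The exact type I error exceeds 0.05 at every N from 25 to 30 except 28.
- If alpha 0.05 governs, power at 0.85 lies between 62% (N=27) and 76% (N=28), and the statement that the sample is large enough is unsupported.

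These results are exact binomial calculations on the plan's own inputs and need no outside assumption. The second-set figures do rest on one: that the first set's expected evaluable fraction carries over. The main finding does not depend on it.

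**What to change.** Choose one rule and give it its own figures.

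- **Option (a), 80% interval.** State one-sided alpha as 0.10 and replace the 90% interval and its formula with Beta(0.10, X, N+1−X). The quoted power can stay (61.7% at N=25 rounds to 62%). Add that power at 0.85 dips to 76.5% at N=28.
- **Option (b), alpha 0.05 with the 90% interval.** Delete the 80% sentence. Restate power as 42/68/90% (N=25) and 43/71/93% (N=30). Withdraw or justify the sentence on sufficient sample size.

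Under either option:

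- List the minimum number of successes for N = 25, 26, 27, 28, 29, 30: 20, 21, 22, 23, 23, 24 under (a), or 21, 22, 23, 23, 24, 25 under (b).
- Document, with a date, which rule applied to the first set. If it cannot be shown to predate the first-set results, report the verdict under both rules.
- For the second set, give cut-offs and power for N = 21 to 25 under the chosen rule, or call that analysis descriptive. The cut-offs are 18, 18, 19, 20, 20 under (a) and 18, 19, 20, 21, 21 under (b).

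**Cost.** Wording and a short table; no extra patients. Option (a) means admitting a less favourable alpha, and option (b) a less favourable power. If the team wanted the conventional 80% power at 0.85 under (b), the smallest set that reaches it is 32 evaluable patients (26 successes needed, 80.5%), above the planned maximum of 30. Power stays at or above 80% only from 39.
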